12.2. Clinical Laboratory Sampling

Subjects that do not have their Visit 1 the same day as Visit 13 of either A-101-WART 301 or A-101-WART 302 will have to have a clinical chemistry and CBC performed. Non-fasting blood samples for clinical laboratory analysis will be collected by a qualified staff member on Day 182 for all subjects. Approximately 7.5 mL of blood will be collected for each chemistry sample and 3 ml of blood will be collected for each complete blood count (CBC). These blood samples will be sent to a central laboratory for analysis. Refer to the study specific laboratory manual for instructions regarding handling of the blood samples and shipping instructions.

The following tests, at a minimum, will be conducted:

Chemistry Panel	Complete Blood Count
Albumin	Hematocrit
Alkaline phosphatase	Hemoglobin
Alanine aminotransferase (ALT)	Platelet count
Aspartate aminotransferase (AST)	Red blood cell morphology
Blood urea nitrogen (BUN)	Red blood cell count
Bicarbonate	White blood cell count
Calcium	White blood cell differential
Chloride	% & absolute
Creatinine	Basophils
Glucose	Eosinophils

Aclaris Therapeutics, Inc.

Protocol Number: A-101-WART-303

Protocol Version 3: 14 February 2019

Lactate dehydrogenase (LDH)	Lymphocytes
Phosphorus	Monocytes
Potassium	Neutrophils
Sodium	
Total bilirubin	
Total protein	
Uric acid	

The results of the clinical laboratory tests will be reported on the central laboratory's standard reports. These laboratory results will be sent to the investigator via fax. The investigator must review all laboratory reports in a timely manner and note NCS or CS to define the clinical relevance of any result that is outside the normal range for the laboratory. The investigator must date and initial every laboratory report.

The investigator must report all laboratory results that are BOTH outside the normal range for the laboratory AND, in the opinion of the investigator, CS as medical history if found prior to the first study medication treatment or as an AE if found after the first study medication treatment begins.

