14.4. Statistical Analysis of Safety Data

Unless otherwise stated, all safety summaries will be conducted using the ITT population. All safety summaries will be produced for the following groups:

- Subjects treated in the study that were randomized to active treatment during the previous A101-WART 301/302 study.
- Subjects treated in the study that were randomized to vehicle during the previous A101-WART 301/302 study.
- Subjects treated in the study overall.
- Subjects not requiring treatment during the study that were randomized to active treatment during the previous A101-WART 301/302 study.
- Subjects not requiring treatment during the study that were randomized to vehicle during the previous A101-WART 301/302 study.
- Subjects receiving active treatment during the study or the previous A101-WART 301/302 study.

The proportion of subjects with treatment emergent adverse events will be tabulated and presented by System Organ Class and Preferred Term from the Medical Dictionary for Regulatory Activities (MedDRA). Likewise, the proportion of subjects with serious AEs will be summarized. Adverse event summaries will be presented showing the proportion of subjects experiencing adverse events, both overall and by MedDRA System Organ Class. The version of MedDRA to be used for the analysis of this study will be specified in the SAP.

Aclaris Therapeutics, Inc.

Protocol Number: A-101-WART-303

Protocol Version 3: 14 February 2019

Local skin reaction (LSR) scores and clinically relevant abnormal laboratory results will be tabulated and presented at the subject level. For each LSR sign and at each in-house visit, the proportion of subjects who had at least one treated wart with LSR severity ≥ 1 will be summarized.

Safety summaries will be supported by listings of all adverse events, laboratory results, and LSR data.

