### **3.11.2 Adverse Events**

Adverse events are coded using the MedDRA (Version 22) and are categorized by system organ class (SOC) and preferred term (PT). Only treatment emergent adverse events are included in summary tabulations (i.e. adverse events occurring within 30 days of each application of study medication). All adverse events are included in the data listings including those that are not considered treatment emergent.

To allow differentiation as to which study period an Adverse Event occurred, three categories are defined based upon onset date. Adverse Events that had onset dates prior to the first application of study medication are considered "prior". Adverse events with onset dates on or within 30 days of an application of study medication are considered "treatment emergent". Events with onset dates more than 30 days after the most recent application of study medication are considered as "post-therapy." In this study, subjects can possibly receive medication up to three cycles and multiple doses of medication within a treatment cycle. The above rule will be applied to all known doses of medication while determining study period.

Frequency tabulations are presented by MedDRA SOC and preferred term, for all adverse events; study treatment-related adverse events, adverse events resulting in discontinuation of study treatment, serious adverse events and adverse events by maximum severity. Adverse events resulting in discontinuation are those with 'action taken' recorded as 'drug withdrawn'.

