### **3.11.4 Laboratory Evaluations**

Shift tables showing changes in relationship to the normal reference range grade from baseline to the "worst" relationship recorded post-baseline are tabulated. In the event a subject had both "low" and "high" post-baseline values the subject will be counted under both "low" and "high". As such, the percentages of the cells in the shift table may add to more than 100%.

Chemistry and hematology parameters will be summarized using descriptive statistics for each visit. Both actual values and changes from baseline will be summarized.

The number and percentage of subjects meeting criteria for hepatobiliary abnormalities will be provided.

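### The SAP drops the protocol's table of clinically relevant laboratory abnormalities without logging it, and the AE tables cover Day 182 findings only when the last application was about Day 152 or later

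*Protocol*

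**What the plan says.** Protocol 14.4 commits to a table: "Local skin reaction (LSR) scores and clinically relevant abnormal laboratory results will be tabulated and presented at the subject level". It treats listings as a separate item: "Safety summaries will be supported by listings of all adverse events, laboratory results, and LSR data". A listing of laboratory results therefore does not meet the first commitment.

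Protocol 12.2 has the investigator mark each out-of-range result as clinically significant (CS) or not (NCS). A result that is both out of range and CS is to be reported "as an AE if found after the first study medication treatment begins". The same section and Table 2 place the scheduled on-study sample at Day 182. A Visit 1 sample is added for subjects whose entry visit does not coincide with the last parent-study visit.

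SAP 3.11.4 lists three laboratory outputs:

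- "Shift tables showing changes in relationship to the normal reference range grade from baseline" to the worst post-baseline category
- "Chemistry and hematology parameters will be summarized using descriptive statistics for each visit", as values and changes from baseline
- the number and percent of subjects meeting hepatobiliary criteria

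SAP 3.11.2 restricts the AE tables: "Only treatment emergent adverse events are included in summary tabulations". Treatment emergent means an onset on or within 30 days of an application. Later events are classed as post-therapy and appear only in listings. SAP 3.14, the log of changes to the planned analysis, records only the move from the ITT to the Safety Population.

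**The concern.** Long-term safety is the primary objective, and clinical laboratory tests are one of the named safety measures. The protocol asks for a summary based on clinical relevance. The SAP's laboratory summaries rest on the reference range, apart from the descriptive statistics and the hepatobiliary count. A shift table counts a value just outside the range exactly as it counts one the investigator judged important.

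The natural reply is that CS results become AEs and are counted there. That works only if the AE is treatment emergent. The one scheduled post-baseline sample comes at the end of the study, often well after the last application. At stake is whether a reader of the summary tables can see how many treated subjects had a laboratory finding judged clinically significant. The change log would not tell that reader that the planned table is gone.

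**Working it through.** **Plan's own figure.** The sample-size section (Protocol 14.1, SAP 3.13) gives 200 × (1 − 0.26) = 148 subjects needing treatment among those previously on active. This reproduces. It says nothing about how many courses each subject receives, and the finding does not depend on it.

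**Planned output against SAP output.**

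| Output | Uses the CS judgement? |
|---|---|
| Protocol 14.4 subject-level table | Yes: clinically relevant results |
| SAP 3.11.4 shift tables | No: position against the normal range |
| SAP 3.11.4 descriptive statistics | No |
| SAP 3.11.4 hepatobiliary count | No: meeting criteria, liver-related only |
| SAP 3.11.2 AE tables | Indirectly, within 30 days of an application |
| AE listings | Indirectly, any onset, but no counts |

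**Inputs for the AE route.**

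- The last scheduled application is on Day 53 of a course (Protocol 10.5), so last application = start day + 52. A +1 day window applies.
- The sample is at Day 182, with an end-of-study window of +2 days.
- The treatment-emergent limit is 30 days (SAP 3.11.2).
- The latest course start is Day 122 (Protocol 6, SAP 3.3).
- Assumption: the onset date of the AE is the sampling date.

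**Gap = 182 − (start + 52).**

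| Course start | Last application | Gap to Day 182 | Class under SAP 3.11.2 |
|---|---|---|---|
| Day 1 | Day 53 | 129 days | post-therapy |
| Day 60 (second course, back-to-back) | Day 112 | 70 days | post-therapy |
| Day 100 | Day 152 | 30 days | treatment emergent |
| Day 119 (third course, back-to-back) | Day 171 | 11 days | treatment emergent |
| Day 122 | Day 174 | 8 days | treatment emergent |

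**Cut-off.** The last application must be on or after Day 182 − 30 = 152. For a full course that means a start on or after Day 152 − 52 = 100, or Day 99 with the +1 window. If the end-of-study visit is on Day 184, the cut-off moves to Day 154 and the start to Day 102 (Day 101 with the +1 window).

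**How many subjects?** The documents give no distribution of courses. For illustration, take subjects treated from Day 1 in back-to-back full courses. Let c be the per-course probability of clearing all warts, and u the uptake of the next course among those not clear. The share not reaching a third course, whose Day 182 AE would be post-therapy, is 1 − ((1 − c) × u)².

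- c = 0.26, u = 1.0: 1 − 0.74² = 45%
- c = 0.26, u = 0.8: 1 − 0.592² = 65%
- c = 0.10, u = 1.0: 1 − 0.90² = 19%
- c = 0.60, u = 0.6: 1 − 0.24² = 94%

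Both c and u are assumptions. The 26% in the plan is a wart-level rate from the parent studies, borrowed here only as a reference point.

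**The case against.** The strongest reply is that nothing is lost except a label. A reportable CS result is by definition out of range, so in a treated subject it feeds the shift table. It also enters the descriptive statistics and, for liver results meeting the criteria, the hepatobiliary count. If reported as an AE, it is in the listings whatever its onset. A reader might infer that such results appear in no summary table at all, and this reply defeats that inference. It does not restore a count of results judged CS.

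A reader might also infer that most treated subjects are affected. The documents do not support that: the illustration runs from 19% to 94%, and third courses and late first courses fall inside the 30-day window. Nor do they show that CS results would be swamped by chance out-of-range values. They give no reference-range coverage, and the shift tables compare results with each parameter's own range rather than pooling the panel.

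Two further points carry some weight. Protocol 14.4 fixes no layout, and Section 14 leaves details to the SAP. That gives the SAP freedom over format, but SAP 3.11.4 contains the table in no format. Second, it is not certain that the CS mark reaches the database: 12.2 describes it as made on the laboratory report. Protocol 13.1.1 also asks for a diagnosis, when certain, in place of laboratory values, so the AE form may lack the parameter and direction. This limits how fine a restored table can be. It does not justify leaving the table out unlogged.

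The SAP also refers to a separate data-handling and programming document that is not available here. SAP 3.11 describes it as holding data-handling rules, so it is an unlikely place for a planned safety table.

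**Conclusion.** The point holds in this form. The protocol's subject-level table of clinically relevant laboratory abnormalities has no counterpart in SAP 3.11.4, and SAP 3.14 does not log its removal. The AE tables replace it only for subjects whose last application was about Day 152 or later. For anyone treated once from Day 1, or twice back-to-back, a clinically significant Day 182 result is not identified as such in any summary table. It shows only as an out-of-range value in the laboratory summaries and as a post-therapy event in the AE listings.

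The gap is one of reporting, not of data collection. The day arithmetic assumes full courses on schedule and an AE onset equal to the sampling date. A course cut short because the warts cleared moves the last application earlier and widens the gap. The number of subjects affected cannot be fixed from the documents.

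**What to change.** Add one table to SAP 3.11.4: the number and percent of treated subjects with at least one post-baseline laboratory result judged clinically significant, by treatment group and regardless of time since the last application. Break it down by parameter and direction if the CS mark is in the database.

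If the mark is not in the database, count subjects with laboratory-related AEs of any onset, including post-therapy, from the AE CRF. A footnote should say that events reported as a diagnosis may lack parameter and direction.

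If the sponsor prefers to keep the omission, SAP 3.14 should record it with a reason.

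The cost is one table and a sentence or two in the SAP. The sponsor should first check whether the CS mark is captured electronically, because that decides which version can be produced.

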14.5. Interim Analysis

No formal interim analysis will be conducted for this study.

15. QUALITY CONTROL AND QUALITY ASSURANCE

15.1. Protocol Amendments

No changes from the final approved (signed) protocol will be initiated without the prior written approval or favorable opinion of a written amendment by the IRB/EC, except when necessary to eliminate immediate safety concerns to the study subjects or when the change involves only logistics or administration. The principal investigator and the sponsor will sign the protocol amendment.

15.2. Protocol Violations

A **protocol violation** is defined as any divergence from the protocol-specific inclusion/exclusion criteria, subject is administered a prohibited medication, and/or GCP guidelines. Protocol violations will be identified and recorded, by study center personnel, on the CRF.

As a matter of policy, sponsor/CRO will not grant **exceptions** to protocol-specific entry criteria to allow patients to enter a study. If under extraordinary circumstances such action is considered ethically, medically, and scientifically justified for a particular patient, prior approval from sponsor/CRO and the responsible IRB/IEC, in accordance with the Sponsor/CROs Standard Operating Procedure (SOP), is required before the patient will be allowed to enter the study. If investigative center personnel learn that a patient who did not meet protocol eligibility criteria was entered in a study (a protocol violation), they must immediately inform sponsor/CRO. Such subjects will be discontinued from the study, except in a rare instance following review and written approval by sponsor/CRO and the responsible IRB/IEC, according to the applicable SOP.

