7.2. Exclusion Criteria

Subjects are excluded from this study if any of the following criteria is met:

1. Subject has clinically atypical warts.
2. Subject is immunocompromised (e.g., due to chemotherapy, systemic steroids, genetic immunodeficiency, transplant status, etc.).
3. Subject has a history of Human Immunodeficiency Virus (HIV) infection.
4. Subject has had any Human Papilloma Virus (HPV) vaccine within 6 months prior to Visit 1.
5. Subject has used any of the following intralesional therapies within the specified period prior to Visit 2:
 - Immunotherapy (e.g., *Candida* antigen, mumps antigen, *Trichophyton* antigen); 8 weeks
 - Anti-metabolite therapy (e.g., bleomycin, 5-fluorouracil); 8 weeks
6. Subject has used any of the following systemic therapies within the specified period prior to Visit 2:
 - Immunomodulatory/immunosuppressant therapy (e.g., etanercept, alefacept, infliximab); 16 weeks
 - Glucocortico-steroids (inhaled and intra-nasal steroids are permitted); 28 days
7. Subject has used any of the following topical therapies within the specified period prior to Visit 2 on, or in the proximity to any of the common warts identified for treatment, that in the investigator's opinion interferes with the study medication treatment or the study assessments:

- LASER, light or other energy-based therapy (*e.g.*, intense pulsed light [IPL], photodynamic therapy [PDT]); 180 days
- Immunotherapy (*e.g.*, imiquimod, squaric acid dibutyl ester [SADBE], etc.) 12 weeks
- Liquid nitrogen, electrodesiccation, curettage; 60 days
- Hydrogen peroxide; 90 days (other than IP from the 301/302 study)
- Antimetabolite therapy (*e.g.*, 5-fluorouracil); 8 weeks
- Retinoids; 90 days
- Over-the-counter (OTC) wart therapies and cantharidin; 28 days

8. Subject currently has or has had any of the following within the specified period prior to Visit 1 on or in the proximity to any of the common warts identified for treatment that, in the investigator's opinion, interferes with the study medication treatment or the study assessments:

- Cutaneous malignancy; 180 days
- Sunburn; currently
- Pre-malignancy (*e.g.*, actinic keratosis); currently

9. Subject has a history of sensitivity to any of the ingredients in the study medications.

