7.3. Removal of Subjects from Study Therapy

A subject may be removed from the study therapy for a variety of reasons, including:

- Unacceptable adverse event
- Subject unwilling or refusal to continue with the protocol defined study visits and/or consent withdrawal for study participation
- Change in compliance with an inclusion/exclusion criteria
- General or specific changes in the subject's condition that render the subject unacceptable for further treatment in this study in the judgement of the investigator.

If a subject is to be withdrawn from the study, the Aclaris Therapeutics, Inc. CRA or designee must be informed within 24 hours of the decision to remove the subject from the study.

Aclaris Therapeutics, Inc.

Protocol Number: A-101-WART-303

Protocol: Version 3: 14 February 2019

The study may be discontinued at the discretion of Aclaris Therapeutics, Inc. Some examples of reasons for discontinuation are the occurrence of the following:

- Increased frequency, severity or duration of known AEs
- Medical, regulatory or ethical reasons affecting the continued performance of the study
- Difficulties in the recruitment of subjects

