7.4. Withdrawal Procedures

If a subject withdraws from the study prior to Day 182 (6-month time-point), the reason for withdrawal and the date of withdrawal from the study must be recorded on the eCRF. If the reason for withdrawal is an adverse event or a clinically significant abnormal laboratory test result, monitoring of the subject will continue until the event has resolved or stabilized, until the patient is referred to the care of a local health care professional, or until a determination of a cause unrelated to the study drug or study procedure is made.

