⁴ Investigational site staff will be required to make a phone contact with the subject on Day 15, Day 43, Day 102 and Day 144 to assess for any safety issues and possible new concomitant medications the subject may have started taking. In addition, subjects are to ask if they have had any new warts develop since the last in office visit.

⁵ Subjects over the age of 18 are to apply the A-101 study medication on the following days: Day 1, Day 4, Day 8, Day 11, Day 15, Day 18, Day 22, Day 25, Day 29, Day 32, Day 36, Day 39, Day 43, Day 46, Day 50 and Day 53. A window of +1 day is allowed. Subject between the ages of 1-17 will have their A-101 study medication applied by a parent or guardian. Parents/legal guardians of children must ensure that the child does not put the treated area in their mouth, or eyes, until completely dry after the application. If the treated area is not completely dry 10 minutes after the application, the area should be blotted dry.

⁶ A-101 will only be dispensed to subjects who have not cleared all their warts, or who have developed new warts, and will be starting a new 8-week treatment cycle.

Table 3 Safety Observation Assessments for Subjects that are Clear at Visit 1 and Remain Clear

Visit	V1	V2	V3	V4	EOS
Treatment Day	Day 1	Week 6 (Day 42)	Week 12 (Day 84)	Week 18 (Day 126)	Week 26 (Day 182)
Window		+7 Days	+ 7 Days	+ 7 Days	+ 2 Days
In Office Visit	▲ ¹				▲

Aclaris Therapeutics, Inc.

Protocol Number: A-101-WART-303

Protocol: Version 3: 14 February 2019

Visit	V1	V2	V3	V4	EOS
Phone Call		▲ ²	▲ ²	▲ ²	
Informed Consent	▲				
Inclusion Criteria/Exclusion Criteria	▲				
Concomitant therapies		▲	▲	▲	▲
Adverse Events	▲	▲	▲	▲	▲

¹Visit 1 of A-101-WART 303 may occur on the same day as Visit 13 of A-101-WART 301 or A-101-WART 302.

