12.1. Local Skin Reactions (LSRs)

The LSR assessment is the Investigator's assessment of the signs and the subject's assessment of the symptoms associated with irritation at the identified common wart site (*i.e.*, the common wart and the skin immediately surrounding the common wart exposed to study medication).

The Local Skin Reaction signs to be assessed are:

- Erythema
- Edema
- Erosion
- Ulceration
- Vesicles/bullae
- Excoriations
- Scabbing

The Local Skin Reaction symptoms to be assessed (by the Subject) are:

- Stinging/burning
- Pruritus (itch)

The Investigator will evaluate the LSR signs at the each identified common wart site as follows:

- At visits where a study medication treatment or retreatment is performed:
 - Perform an LSR assessment prior to any study medication application
 - and

The Subject will assess the LSR symptoms at the identified common wart site as follows:

- At visits where a study medication treatment or retreatment is performed:
 - Perform an LSR assessment prior to any study medication application

At visits where **NO** study medication treatment is performed:

- Perform an LSR assessment.

Subjects are to remain in the clinic for 20 minutes after the application of their study medication. Any local skin reactions or other adverse experiences that occur during this time period must be

Aclaris Therapeutics, Inc.

Protocol Number: A-101-WART-303

Protocol Version 3: 14 February 2019

documented as an adverse event.

The Investigator and Subject should report the one integer that best describes the severity of each LSR sign or LSR symptom for the common wart site using the scale below:

Local Skin Reactions	
Grade	Descriptor
0	None OR No signs or symptoms present.
1	Asymptomatic or mild symptoms OR clinical or diagnostic observations only OR intervention not indicated.
2	Moderate OR minimal, local or noninvasive intervention indicated.
3	Severe or medically significant but not immediately life threatening OR disabling OR limiting self-care of activities of daily living.

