#### 3.2 Treatment Groups and Data Presentation

This is an open-label study with only one treatment arm. Subjects who enter the study with a common wart receive study medication immediately. Subjects who enter the study with no common warts do not receive study medication at the start and will not be treated at all if they do not develop any common warts throughout the course of the study. In order to be eligible for this study, subjects must have completed protocol treatment on either the A-101-WART-301 or A-101-WART-302 study. Both WART-301 and WART-302 were double-blind studies where subjects were treated with either active A-101 45% topical solution or vehicle solution. To best account for all potential exposure to A-101 45%, summaries and analyses will take into consideration both the current open-label treatment status as well as the randomized treatment assignment from the subject's respective double-blind study. This classification precipitates the following four treatment groups.

- Open Label A-101 45%: Double-Blind A-101 45%
- Open Label A-101 45%: Double-Blind Vehicle
- Open Label Not Treated: Double-Blind A-101 45%
- Open Label Not Treated: Double-Blind Vehicle

Depending upon analysis population, data will be summarized into all or a subset of treatment groups indicated above. Summaries on All Enrolled Population will display all four treatment groups. Summaries on Safety Population will display only first two treatment groups.

All data listings will be sorted by treatment group and subject ID. Subject ID will identify site number and double-blind study subject participated prior to open label study

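### Protocol 15.2 by default takes subjects found ineligible after dosing out of the study, not only off A-101, so their scheduled safety follow-up stops while they stay in the Safety Population

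*Protocol*

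**What the plan says.** **Removal.** Protocol 15.2 covers a patient who was entered without meeting the eligibility criteria: "Such subjects will be discontinued from the study, except in a rare instance following review and written approval by sponsor/CRO and the responsible IRB/IEC". The sentence does not separate dosed from undosed subjects, and it does not offer stopping the drug with observation continuing. Protocol 7.3 is worded differently. It begins "A subject may be removed from the study therapy for a variety of reasons, including", and one listed reason is "Change in compliance with an inclusion/exclusion criteria". That is permissive and concerns therapy, although 7.3 says nothing about follow-up once therapy stops.

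**After withdrawal.** Protocol 7.4 asks for the reason and date, then adds: "If the reason for withdrawal is an adverse event or a clinically significant abnormal laboratory test result, monitoring of the subject will continue". No other withdrawal reason carries that duty. Tables 2 and 3 contain no early-termination visit. SAP Appendix A can place early-termination data in an analysis visit, but nothing in the protocol requires those data to be collected.

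**Reporting periods.** Under 13.1.3, non-serious AEs are reported up to the last study visit; after it, only SAEs judged related are reported. Under 13.2.1 and 13.2.2, open related AEs and ongoing SAEs are followed to a stable outcome.

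**Analysis.** SAP 3.1 defines the Safety Population by at least one application. SAP 3.9 only lists protocol violations. SAP 3.5 lists each discontinuation with its reason and the duration of treatment.

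**The concern.** The primary objective is long-term safety, and Protocol Section 6 expects every subject to stay on study for six months. A dosed subject later found ineligible has been exposed and counts in the denominator, but scheduled collection stops at removal.

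The main route is ineligibility that comes to light after dosing, such as medical history not disclosed at Visit 1. Some of the criteria bear directly on safety: immunocompromise (exclusion 2), sensitivity to an ingredient (exclusion 9) and skin disease that puts the subject at undue risk (exclusion 10). A dosed subject with one of these is someone to keep watching, for the subject's own protection as well as for the data.

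The bias runs one way: uncollected events can only lower observed incidence. The SAP 3.5 listing shows that follow-up was cut short but does not recover the data.

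**Working it through.** **1. The plan's figure.** Protocol 14.1 and SAP 3.13 expect 200 prior-active subjects with 26% clear: 200 x (1 - 0.26) = 148. This reproduces. It counts prior-active subjects only. Both sections expect some prior-vehicle subjects to be treated as well, and SAP 3.1 includes them, so 148 is a lower bound on the safety denominator.

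**2. What removal loses and keeps.**

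| Item | After removal under 15.2 |
|---|---|
| Events up to removal | Kept |
| Open related AEs, ongoing SAEs, later related SAEs | Kept (13.1.3, 13.2.1, 13.2.2) |
| New non-serious AEs, including the rest of the 30-day treatment-emergent window | Lost |
| Later unrelated SAEs | Lost |
| Remaining LSR scores (scheduled Days 29, 60, 182) | Lost |
| Day 182 chemistry and CBC, the only scheduled post-baseline sample | Lost |

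**3. Number affected.** The documents give no rate. Assume 2-5% of 148: 2.96 and 7.4, so about 3 to 7 subjects (3/148 = 2.03%; 7/148 = 4.73%).

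**4. AE incidence.** Assume 10% incidence over a full course and a constant event rate. The last application of a course is on Day 53 and SAP 3.11.2 adds 30 days, so a full course carries 53 + 30 = 83 days at risk. Removal on the day of the last application loses the 30 days after it. The loss per affected subject is 10% x 30/83 = 3.6%, whatever the removal day.

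- 3 subjects: 3/148 x 3.6% = 0.07 points
- 7 subjects: 7/148 x 3.6% = 0.17 points

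Exponential check: the daily rate is -ln(0.9)/83 = 0.00127. For removal on Day 15, exp(-15 x rate) - exp(-45 x rate) = 0.9811 - 0.9445 = 0.0367, which gives 0.074 and 0.173 points. For Day 53 the difference is 0.9349 - 0.9000 = 0.0349, which gives 0.071 and 0.165 points.

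**5. LSR incidence.** The Day 1 score is taken before application and serves as baseline, so removal before Day 29 leaves no scheduled post-baseline score. At an assumed 50% incidence of worsening, the upper limit with all removals before Day 29 is 3/148 x 50% = 1.0 points and 7/148 x 50% = 2.4 points. If half are removed before Day 29 and the rest had already shown any worsening by then, the limits halve to 0.5 and 1.2 points.

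**6. Rare events and target.** The 95% upper bound for an event never seen is 1 - 0.05^(1/n). It is 2.00% at n = 148 and 2.10% at n = 141 (148 - 7). The 141 is still above the target of 100.

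**7. What continued follow-up would add.** After a last dose on Day 15, 182 - 15 = 167 days remain. The treatment-emergent window ends on Day 45, so AEs in the other 182 - 45 = 137 days would be listed only. Of the LSR visits, Day 29 (14 days after the dose) falls within the SAP's 30-day summary; Days 60 and 182 (45 and 167 days after) count only in the any-time summary.

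**The case against.** **The trigger.** A reader might infer that the eligibility timing builds in frequent removals after dosing. Exclusion 6, for example, reads "Subject has used any of the following systemic therapies within the specified period prior to Visit 2", exclusions 5 and 7 use the same reference point, and Visit 2 is Day 15. SAP 3.2 states: "Subjects who enter the study with a common wart receive study medication immediately". Applications on Days 1, 4, 8 and 11 thus precede the visit from which the look-back runs. The documents do not support the stronger inference. Protocol 11.1 has the investigator ask about these therapies at Visit 1, so earlier use can be known before dosing. Use that begins after Visit 1 fits 7.3's change in compliance better than 15.2's patient who did not meet the criteria when entered. The look-back is only a secondary route.

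**The size.** A reader might also infer that early removal costs more, because a Day 15 stop loses 30/45 = 67% of that subject's treatment-emergent window. That share is right, but a subject with 45 days at risk does not carry the full-course 10% incidence. Under a constant rate, the 30 lost days cost the same at any removal day.

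**What is still collected.** Protocol 12.1 adds: "Subjects are to remain in the clinic for 20 minutes after the application of their study medication", and reactions in that time are recorded as AEs. In Table 2, footnote 4, sites must "make a phone contact with the subject on Day 15, Day 43, Day 102 and Day 144 to assess for any safety issues", so a subject still on study at Day 15 has had one safety call. Much of the lost period is off drug and would be listed only. The Day 182 sample could come 167 days after the last dose.

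**Policy.** 15.2 has an exception that could retain a dosed subject, and it refers to an SOP not available here. 7.3 is not a contrary rule that 15.2 breaks, since 7.3 specifies no follow-up either.

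**What stands.** These arguments limit the size and the urgency. They do not close the gap: the exception is described as rare and needs case-by-case written approval, and no clause in either document keeps these subjects under scheduled observation.

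**Conclusion.** The gap is real. Followed as written, the plan stops collecting scheduled safety data on some exposed subjects while counting them in the safety denominator. The direction is toward understatement.

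The effect is small: about 0.07-0.17 points on AE incidence at any removal day, and at most about 1.0-2.4 points on LSR incidence. These figures rest on assumptions the documents do not supply: 2-5% affected, 10% AE incidence at a constant rate with removal on the day of the last application, and 50% LSR incidence with all removals before Day 29. A larger denominator from treated prior-vehicle subjects leaves the point estimates unchanged at the same affected share, and lowers the zero-event bound.

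It would be wrong to conclude that safety reporting for these subjects ends altogether, or that the study's safety conclusions or its target of 100 are at risk. The reason to change the text is that it runs against the primary objective, may drop subjects at higher risk, and is cheap to put right.

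**What to change.** Amend 15.2: for a subject who has had at least one application, an eligibility breach may stop A-101 (investigator and medical monitor to decide), but the already scheduled AE and LSR assessments and the Day 182 laboratory sample continue, unless consent is withdrawn or valid consent or assent was never obtained. Subjects not yet dosed may still be removed. Align 7.4 so that continued follow-up is not confined to AE and laboratory withdrawals. The SAP needs no change.

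Cost: an amendment with IRB approval under 15.1, and a few continued visits for a small number of subjects. These include one blood draw of about 10.5 mL (7.5 + 3 mL, Protocol 12.2), a real if modest burden in a study open to children from one year of age.
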